- For patients who are HBsAg negative and HBcAb positive, perform monthly HBV DNA monitoring until 12 months after the last dose of obinutuzumab or placebo. Patients who are HCV positive with no detectable HCV RNA at least 6 months after completion of antiviral therapy are eligible but will require monthly HCV RNA monitoring until 12 months after the last dose of obinutuzumab or placebo. For applicable sites, monthly HBV DNA monitoring and monthly HCV RNA monitoring can be done using mobile nursing.
- ^p Antibody titers include mumps, rubella, Varicella, tetanus, and Streptococcus pneumoniae, as available per laboratory facility.
- 9 Samples will be drawn before administration of study drug infusions on dosing days.
- ^r Autoantibodies include ANA, anti-dsDNA, Sm, Ro, La, and RNP.
- Antiphospholipid antibodies include anti-cardiolipin and anti-β-2-glycoprotein antibodies.
- At infusion visits, obtain pre-infusion (recommended to be collected simultaneously with the earlier blood draw [prior to premedication] for the sake of patient comfort) and at the end of infusion (or within 30 minutes after the end of infusion). The timing of the PK sampling pre- and post-infusion should be precisely recorded. At non-infusion visits a single sample will be obtained.
- ^u Urine for biomarkers will be processed at the study site. Instructions will be provided in the laboratory manual.
- Concomitant therapy consists of any medication (e.g., prescription drugs, over-the-counter drugs, vaccines, herbal or homeopathic remedies, nutritional supplements) used by a patient in addition to protocol-mandated treatment from 7 days prior to screening to the study completion/discontinuation visit. All such medications should be reported to the investigator and recorded on the Concomitant Medications eCRF. Under certain circumstances, the Medical Monitor may assess that medications used by a patient more than 7 days prior to screening may need to be captured on the Concomitant Medications eCRF (e.g., COVID-19 vaccinations and latent TB treatment must always be captured on the Concomitant Medications eCRF).
- ^w At Week 80, adverse events will be recorded during infusion and post-infusion. For subsequent infusion visits, adverse events will be recorded pre-infusion, during infusion, and post-infusion. For all serious infectious adverse events reported, CBC with differential, quantitative immunoglobulins, and flow cytometry should be measured within 1 week of onset.
- At infusion visits, premedication with acetaminophen 650–1000 mg PO and diphenhydramine 50 mg PO or IV (or equivalent dose of a similar agent) will be given. Premedication with methylprednisolone 80 mg IV should only be given if the patient experienced an infusion-related reaction with the previous infusion. The administration of all premedications should be completed between 30 and 60 minutes prior to the study drug infusion.
- For ex-U.S. sites, IxRS will be contacted in order to confirm MMF dispensing out of the central supply. For U.S. sites, MMF will be supplied locally and IxRS will not need to be contacted.

Table 3 Schedule of Activities for Open-Label Treatment

					Ol	pen-L	abel T	reatm	ent		Unplanned Visit ^a	Study Discontinuation
Week of Open-Label Treatment (OLT)	0 (Day 1)	2	4	12	24	26	36	52	76	Every 6 months thereafter ^b	NA	
IxRS	Χc	x			х	х		х	x	х		х
Assessment of eligibility for open-label treatment ^d	х											
Patient-reported outcomes (SGA, FACIT-F, SF-36 v2, EQ-5D-5L) e	х				х			х	х	х	Χª	х
Clinician-reported outcomes (PGA, SLEDAI-2K)	х				х			х	х	х	Χ ^a	х
Vital signs ^f	х	х	Х		х	х		х	х	х	Х	х
Weight	X a				Хg			χg	χg	Χâ		
Limited physical examination h					х			х	х			х
ECG (12-lead)									x			
Hematology ⁱ	х	x	Х	Х	х	х	Х	x	x	x	χa	x
Chemistry ^j	х	x	X	х	х	х	х	х	X	x	χa	х
Pregnancy test ^k	х	х	Х	х	х	х	х	х	х	х		
Urinalysis ^I	Х		Х	Х	Х		Х	Х	Х	х	Χ ^a	х
24-hour urine collection ^m	X n				Х			Х	Х	х		
HBV DNA/HCV RNA∘		See Footnote o										
Quantitative serum Ig levels	х			х	х			х	х	х		х

Table 3 Schedule of Activities for Open-Label Treatment (cont.)

					0	pen-L	abel T	reatm	ent		Unplanned Visit ^a	Study Discontinuation
Week of Open-Label Treatment (OLT)	0 (Day 1)	2	4	12	24	26	36	52	76	Every 6 months thereafter ^b	NA	
Vaccination antibody titers ^p	х								х			
Hemoglobin A _{1c}	х								х			х
Blood sample for flow cytometry ^q	х		Х	х	х		х	х	х	х	χa	х
High-sensitivity flow cytometry ^q	х		х		х			x	х	х		
Complement (C3, C4 and CH50)	х		Х	х	х			x	х	х	Χa	х
Autoantibody profile ^r	х		х	х	х			X	х	х	Х ^а	х
Antiphospholipid antibodies ⁹	х								х			
Serum PK sample ^t	х	х	х	х	х	х	х	x	х	х	Х ^а	х
Serum ADA sample ^q	х	х		х	х		х	x	х	х	X ^a	х
Plasma sample for biomarkers ^q	х				х			x	х			
Serum sample for biomarkers ^q	х		Х	х	х			x	х		Х ^а	
Urine sample for biomarkers ^u	х		х	х	х			x	х		χa	
Blood sample for RNA ^q	х		х	х	х			х	х			
Concomitant medications v	х	х	х	х	х	х	х	x	х	х	X	х
Adverse events w	х	х	х	х	х	х	х	x	х	х	х	х
Obinutuzumab administration *	х	х			х	х		x	х	х		
MMF dispensing y	х			х	х	х	х	х	х	х		

Table 3 Schedule of Activities for Open-Label Treatment (cont.)

ADA=anti-drug antibody; eCRF=electronic Case Report Form; EQ-5D-5L=EuroQol 5-Dimension, 5-Level Questionnaire; FACIT-F=Functional Assessment of Chronic Illness Therapy–Fatigue; HBcAb=hepatitis B core antibody; HBsAg=hepatitis B surface antigen; HBV=hepatitis B virus; IxRS=interactive Web response system; MMF=mycophenolate mofetil; PGA=Physician's Global Assessment; PK=pharmacokinetic; SF-36 v2=36-Item Short Form Survey, Version 2; SGA=Subject's Global Assessment; SLEDAI-2K=Systemic Lupus Erythematosus Disease Activity Index 2000; UPCR=urinary protein-to-creatinine ratio.

Notes: All assessments will be performed pre-infusion unless otherwise specified. Through OLT Week 76, all visits should be performed within ±3 days of the scheduled visit. However, an interval of 14 days should be kept between paired blinded obinutuzumab infusions (OLT Days 1 & 14 (OLT Week 2); OLT Days 168 (OLT Week 24) & 182 (OLT Week 26); OLT Days 350 (OLT Week 50) & 364 (OLT Week 52), i.e. second of a course of two 6 monthly infusions interspersed by 2 weeks ('paired infusions'). Subsequent visits should be performed within ±7 days of the scheduled visit.

- ^a Unplanned visits may be performed if clinically indicated. Adverse events, concomitant medications and vital signs must be assessed for each unplanned visit. Other procedures, tests, and assessments will be performed at the discretion of the investigator. However, in case of a change in lupus symptomatology or a suspected flare, the following tests should be performed for study purposes: urinalysis including UPCR, chemistry panel, hematology panel, flow cytometry, clinician reported outcomes (PGA and SLEDAI-2K), autoantibodies, complement C3 and C4 as well as samples for pharmacokinetics and ADA assessments. Any unplanned laboratory samples should also be sent to the central laboratory per instructions in the laboratory manual.
- b After Week 76 of OLT, visits will occur approximately every 6 months as follows: at OLT Weeks 102 and 128 for Year 3 of OLT; at Weeks 154 and 180 for Year 4 of OLT, and at OLT Weeks 206 and 232 for Year 5 of OLT.
- ^c For patients who enter OLT directly after Week 76, OLT will begin on Week 80 (OLT Day 1 [Week 0]). At this visit, IxRS will be contacted to confirm the start of OLT. OLT may only be initiated once 60 days have elapsed from the most recent obinutuzumab or placebo infusion.
- d Patients may enter OLT if they meet inadequate response criteria at Week 76 or if there is loss of response during blinded treatment after Week 80. Refer to Section 3.1.3 for details.
- ^e Patient-reported outcomes will be performed prior to other assessments and procedures.
- f Blood pressure and pulse rate (while patient is seated for 5 minutes), respiratory rate, and body temperature. Vital signs should be taken pre-infusion, then in seated or semi-supine position, every 15 minutes for 1 hour, then every 30 minutes until the end of the infusion, and within 30 minutes post-infusion. Additional readings may be obtained at the discretion of the investigator.
- ^g While the patient weight should be measured in order for the central lab to have the information available, for these specific visits (Weeks 0 [Day 1], 24, 52, 76, and every 6 months thereafter) it does not need to be captured in the eCRF.

Table 3 Schedule of Activities for Open-Label Treatment (cont.)

- Limited, symptom-directed physical examinations should be performed at specified post baseline visits and as clinically indicated. Changes from baseline abnormalities should be recorded in patient notes. New or worsened clinically significant abnormalities should be recorded as adverse events on the Adverse Event eCRF.
- Hematology: CBC, RBC count, WBC count and differential, hemoglobin, hematocrit, mean corpuscular volume, mean corpuscular hemoglobin, and quantitative platelet count.
- Serum chemistries include AST/SGOT, ALT/SGPT, alkaline phosphatase, total protein, albumin, cholesterol, total bilirubin, BUN, uric acid, creatinine, random glucose, lactate dehydrogenase, potassium, sodium, chloride, calcium, and phosphorus, CPK, cystatin C, and triglycerides.
- For women of childbearing potential, including those who have had a tubal ligation, a negative urine pregnancy test is required prior to all study drug infusions. If a urine test is positive, results will be confirmed with a serum pregnancy test prior to study drug administration. Study drug infusion must not be administered unless the serum pregnancy test result is negative.
- First morning urine sample is preferred. All urinalyses will be analyzed at the central laboratory and include microscopic examination, macroscopic urinalysis, and UPCR.
- ^m To be analyzed for total protein, total creatinine, creatinine clearance, and UPCR.
- " Only required if the Week 76 24-hour urine collection was missing or could not be analyzed.
- For patients who are HBsAg negative and HBcAb positive, perform monthly HBV DNA monitoring until 12 months after the last dose of obinutuzumab or placebo. Patients who are HCV positive with no detectable HCV RNA at least 6 months after completion of antiviral therapy are eligible but will require monthly HCV RNA monitoring until 12 months after the last dose of obinutuzumab or placebo. For applicable sites, monthly HBV DNA monitoring and monthly HCV RNA monitoring can be done using mobile nursing.
- ^p Antibody titers include mumps, rubella, Varicella, tetanus, and Streptococcus pneumoniae, as available per laboratory facility.
- ^q Samples will be drawn before administration of study drug infusions on dosing days.
- ^r Autoantibodies include ANA, anti-dsDNA, Sm, Ro, La, and RNP.
- ^s Antiphospholipid antibodies include anti-cardiolipin and anti-beta-2-glycoprotein antibodies.
- At infusion visits, obtain pre-infusion (recommended to be collected simultaneously with the earlier blood draw [prior to premedication] for the sake of patient comfort) and at the end of infusion (or within 30 minutes after the end of infusion). The timing of the PK sampling pre- and post-infusion should be precisely recorded. At non-infusion visits a single sample will be obtained.
- ⁴ Urine for biomarkers will be processed at the study site. Instructions will be provided in the laboratory manual.

Table 3 Schedule of Activities for Open-Label Treatment (cont.)

- Concomitant therapy consists of any medication (e.g., prescription drugs, over-the-counter drugs, vaccines, herbal or homeopathic remedies, nutritional supplements) used by a patient in addition to protocol-mandated treatment from 7 days prior to screening to the study completion/discontinuation visit. All such medications should be reported to the investigator and recorded on the Concomitant Medications eCRF. Under certain circumstances, the Medical Monitor may assess that medications used by a patient more than 7 days prior to screening may need to be captured on the Concomitant Medications eCRF (e.g., COVID-19 vaccinations and latent TB treatment must always be captured on the Concomitant Medications eCRF).
- ^w At Week 80, adverse events will be recorded during infusion and post-infusion. For subsequent infusion visits, adverse events will be recorded pre-infusion, during infusion, and post-infusion. For all serious infectious adverse events reported, CBC with differential, quantitative immunoglobulins, and flow cytometry should be measured within 1 week of onset.
- At infusion visits, premedication with methylprednisolone 80 mg IV (see note below), acetaminophen 650–1000 mg PO and diphenhydramine 50 mg PO or IV (or equivalent dose of a similar agent) will be given. Beginning at the OLT Week 76 infusion, premedication with methylprednisolone 80 mg IV should only be given if the patient experienced an infusion-related reaction with the previous infusion. The administration of all premedications should be completed between 30 and 60 minutes prior to the study drug infusion.
- For ex-U.S. sites, IxRS will be contacted in order to confirm MMF dispensing out of the central supply. For U.S. sites, MMF will be supplied locally and IxRS will not need to be contacted.

Table 4 Schedule of Activities for the Study Follow-Up Period

		Study	Unplanned visit ^a	Study discontinuation		
				Continued follow-up		
Week of Study Follow-Up (SFU)	0	26	52	visits every 6 months (if needed) b	NA	
MMF dispensing ^c	x	х	x	x		
Vital signs ^d	х	х	x	х	х	х
Hematology ^e	х	х	x	х	X ^a	х
Chemistry ^f	х	х	x	х	X ^a	х
Pregnancy test ^g	х	х	x	х		
Urinalysis h	х	х	х	х	X ^a	х
HBV DNA/HCV RNA i			Se	e Footnote i		
Quantitative serum lg levels	х	х	x	х		х
Vaccination antibody titers j	х	х	x	x		
Blood sample for flow cytometry	х	Х	X	х		
Concomitant medications k	х	Х	X	х	х	х
Adverse events I	х	Х	X	x	х	х

Table 4 Schedule of Activities for the Study Follow-Up Period (cont.)

eCRF=electronic Case Report Form; HBcAb=hepatitis B core antibody; HBsAg=hepatitis B surface antigen; HBV=hepatitis B virus; IxRS=interactive Web response system; MMF=mycophenolate mofetil; NA=not applicable; SFU=study follow-up; UPCR=urinary protein-to-creatinine ratio.

Notes: The first SFU visit will be scheduled approximately 6 months after the previous study visit (e.g., 6 months after Week 76). All visits should be performed within ± 7 days of the scheduled visit.

- ^a Unplanned visits may be performed if clinically indicated. Adverse events, concomitant medications and vital signs must be assessed for each unplanned visit. Other procedures, tests, and assessments will be performed at the discretion of the investigator. However, in case of a change in lupus symptomatology or a suspected flare, the following tests should be performed for study purposes: urinalysis including UPCR, chemistry panel, hematology panel, flow cytometry, clinician reported outcomes (PGA and SLEDAI-2K), autoantibodies, complement C3 and C4 as well as samples for pharmacokinetics and ADA assessments. Any unplanned laboratory samples should also be sent to the central laboratory per instructions in the laboratory manual.
- b For patients with continued lack of peripheral B-cell recovery or who elect for additional SFU, visits will occur approximately every 6 months until study ends (Section 3.1.4).
- ^c For Ex-U.S. sites, IxRS will be contacted in order to confirm MMF dispensing out of the central supply. For U.S. sites, MMF will be supplied locally and IxRS will not need to be contacted.
- d Blood pressure and pulse rate (while patient is seated for 5 minutes), respiratory rate, and body temperature. Additional readings may be obtained at the discretion of the investigator.
- Hematology: CBC, RBC count, WBC count and differential, hemoglobin, hematocrit, mean corpuscular volume, mean corpuscular hemoglobin, and quantitative platelet count.
- f Serum chemistries include AST/SGOT, ALT/SGPT, alkaline phosphatase, total protein, albumin, cholesterol, total bilirubin, BUN, uric acid, creatinine, random glucose, lactate dehydrogenase, potassium, sodium, chloride, calcium, and phosphorus, CPK, and triglycerides.
- ⁹ For women of childbearing potential, including those who have had a tubal ligation, urine pregnancy tests will be performed at specified visits. If urine test is positive, results will be confirmed with a serum pregnancy test.
- ^h First morning urine sample is preferred. All urinalyses will be analyzed at the central laboratory and include microscopic examination, macroscopic urinalysis, and UPCR.
- For patients who are HBsAg negative and HBcAb positive, perform monthly HBV DNA monitoring until 12 months after the last dose of obinutuzumab or placebo. Patients who are HCV positive with no detectable HCV RNA at least 6 months after completion of antiviral therapy are eligible but will require monthly HCV RNA monitoring until 12 months after the last dose of obinutuzumab or placebo.
- Antibody titers include mumps, rubella, Varicella, tetanus, and Streptococcus pneumoniae, as available per laboratory facility.

Table 4 Schedule of Activities for the Study Follow-Up Period (cont.)

- ^k Concomitant therapy consists of any medication (e.g., prescription drugs, over-the-counter drugs, vaccines, herbal or homeopathic remedies, nutritional supplements) used by a patient in addition to protocol-mandated treatment from 7 days prior to screening to the study completion/discontinuation visit. All such medications should be reported to the investigator and recorded on the Concomitant Medications eCRF. Under certain circumstances, the Medical Monitor may assess that medications used by a patient more than 7 days prior to screening may need to be captured on the Concomitant Medications eCRF (e.g., COVID-19 vaccinations and latent TB treatment must always be captured on the Concomitant Medications eCRF).
- For all serious infectious adverse events reported, CBC with differential, quantitative immunoglobulins, and flow cytometry should be measured within 1 week of onset.

Appendix 2 International Society of Nephrology/Renal Pathology Society (ISN/RPS) 2003 Classification of Lupus Nephritis

Table 1 Classifications

Class	Description
Class I	Minimal mesangial LN Normal glomeruli by light microscopy, but mesangial immune deposits by immunofluorescence
Class II	Mesangial proliferative LN Purely mesangial hypercellularity of any degree or mesangial matrix expansion by light microscopy, with mesangial immune deposits A few isolated subepithelial or subendothelial deposits may be visible by immunofluorescence or electron microscopy, but not by light microscopy
Class III	Focal LN Active or inactive focal, segmental or global endo- or extracapillary glomerulonephritis involving < 50% of all glomeruli, typically with focal subendothelial immune deposits, with or without mesangial alterations
Class III (A)	Active lesions: focal proliferative LN
Class III (A/C)	Active and chronic lesions: focal proliferative and sclerosing LN
Class III (C)	Chronic inactive lesions with glomerular scars: focal sclerosing LN
Class IV	Diffuse LN Active or inactive diffuse, segmental or global endo- or extracapillary glomerulonephritis involving ≥50% of all glomeruli, typically with diffuse subendothelial immune deposits, with or without mesangial alterations. This class is divided into diffuse segmental (IV-S) LN when ≥50% of the involved glomeruli have segmental lesions, and diffuse global (IV-G) LN when ≥50% of the involved glomeruli have global lesions. Segmental is defined as a glomerular lesion that involves less than half of the glomerular tuft. This class includes cases with diffuse wire loop deposits but with little or no glomerular proliferation.
Class IV-S (A)	Active lesions: diffuse segmental proliferative LN
Class IV-G (A) Class IV-S (A/C)	Active lesions: diffuse global proliferative LN Active and chronic lesions: diffuse segmental proliferative and sclerosing LN
Class IV-G (A/C)	Active and chronic lesions: diffuse global proliferative and sclerosing LN
Class IV-S (C)	Chronic inactive lesions with scars: diffuse segmental sclerosing LN
Class IV-G (C)	Chronic inactive lesions with scars: diffuse global sclerosing LN
Class V	Membranous LN Global or segmental subepithelial immune deposits or their morphologic sequelae by light microscopy and by immunofluorescence or electron microscopy, with or without mesangial alterations Class V LN may occur in combination with Class III or IV in which case both will be diagnosed. Class V LN may show advanced sclerosis
Class VI	Advanced sclerotic LN ≥ 90% of glomeruli globally sclerosed without residual activity

A=active; C=chronic; G=global; LN=lupus nephritis; S=segmental.

Table 2 Definitions

Term	Definition
Diffuse	A lesion involving most (≥50%) glomeruli
Focal	A lesion involving < 50% of glomeruli
Global	A lesion involving more than half of the glomerular tuft
Segmental	A lesion involving less than half of the glomerular tuft (i.e., at least half of the glomerular tuft is spared)
Mesangial hypercellularity	At least three mesangial cells per mesangial region in a 3 micron thick section
Endocapillary proliferation	Endocapillary hypercellularity due to increased number of mesangial cells, endothelial cells, and infiltrating monocytes, and causing narrowing of the glomerular capillary lumina
Extracapillary proliferation or cellular crescent	Extracapillary cell proliferation of more than two cell layers occupying one fourth or more of the glomerular capsular circumference
Karyorrhexis	Presence of apoptotic, pyknotic, and fragmented nuclei
Necrosis	A lesion characterized by fragmentation of nuclei or disruption of the glomerular basement membrane, often associated with the presence of fibrin-rich material
Hyaline thrombi	Intracapillary eosinophilic material of a homogeneous consistency by which immunofluorescence has been shown to consist of immune deposits
Proportion of involved glomeruli	Intended to indicate the percentage of total glomeruli affected by LN, including the glomeruli that are sclerosed due to LN, but excluding ischemic glomeruli with inadequate perfusion due to vascular pathology separate from LN

LN=lupus nephritis.

Source: Weening JJ, D'Agati VD, Schwartz MM, et al. The classification of glomerulonephritis in systemic lupus erythematosus revisited. J Am Soc Nephrol 2004;15:241–50.

[figure not shown]

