ADA = anti-drug antibody; CKD-EPI = Chronic Kidney Disease Epidemiology Collaboration; CRR = complete renal response; eGFR = estimated glomerular filtration rate; FACIT-F = Functional Assessment of Chronic Illness Therapy–Fatigue; IRR = infusion-related reaction; NCI CTCAE v5.0 = National Cancer Institute Common Terminology Criteria for Adverse Events, Version 5.0; ORR = overall renal response; PK = pharmacokinetic; PRR = partial renal response; SLEDAI-2K = Systemic Lupus Erythematosus Disease Activity Index 2000; ULN = upper limit of normal; UPCR = urinary protein-to-creatinine ratio.

OVERALL DESIGN AND STUDY POPULATION

This parallel-group, double-blind, randomized, placebo-controlled study will compare the efficacy and safety of obinutuzumab versus placebo among patients with ISN/RPS 2003 Class III or IV LN treated with standard-of-care therapy with MMF and corticosteroids.

Several key aspects of the study design and study population are summarized below.

Phase:	Phase III	Population Type:	Adult patients
Control Method:	Placebo	Population Diagnosis or Condition:	Active or active/chronic ISN/RPS Class III or IV proliferative LN
Interventional Model:	Parallel group	Population Age:	18–75 years
Test Compound{s}:	Obinutuzumab	Site Distribution:	Multi-site and multi- region
Active Comparator:	Not Applicable	Study Intervention Assignment Method:	Randomization
Number of Arms:	2	Number of Participants to Be Enrolled:	Approximately 252

STUDY TREATMENT

Obinutuzumab 1000 mg or placebo will be administered by IV infusion during blinded treatment at Day 1 and Weeks 2, 24, 26, 50, and 52. Subsequent blinded infusions will occur at Week 80 and every 6 months thereafter for patients with an adequate response at Week 76. Open-label treatment (OLT) will follow the initial obinutuzumab treatment schedule with infusions on OLT Day 1; at OLT Weeks 2, 24, 26, 52 and every 6 months thereafter.

All patients will receive MMF from the baseline visit (Day 1) onward. MMF will be titrated by Week 4 to a target dose of 2.0–2.5 g/day in divided doses. For patients newly initiating MMF,

the recommended initial dosage is 1.5 g/day given in divided doses with titration by 500 mg/week to 2.0–2.5 g/day by Week 4.

MMF should be maintained at the target dose through Week 80. Adjustments to MMF dosing will be permitted because of intolerance and adverse events. The dosage should not exceed 2.5 g/day unless discussed with the Medical Monitor.

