3.1.3 Open-Label Treatment

For patients with an inadequate treatment response at Week 76, open-label treatment with obinutuzumab will be provided if all of the following criteria are met at Week 76:

- Inadequate treatment response
- Clinically meaningful improvement from baseline in renal parameters or prior clinically meaningful improvement from baseline followed by worsening
- Need for intensification of therapy
- No unmanageable treatment-emergent adverse events
- No rescue therapy (except corticosteroid-only rescue; see Section 4.4.4.1.1) or treatment failure

Documentation of these criteria will be submitted to the Medical Monitor for review. Investigators may discuss the appropriateness of OLT directly with the Medical Monitor if needed. For patients who initiate OLT based on the Week 76 assessment, the first OLT visit (OLT Day 1) will occur on Week 80.

Additionally, patients who, during blinded treatment after Week 80, experience a loss of adequate response requiring intensification of therapy and without unmanageable treatment-emergent adverse events may initiate OLT once 60 days have elapsed from the most recent obinutuzumab or placebo infusion.

During OLT, patients will receive obinutuzumab 1000 mg on OLT Day 1 and OLT Weeks 2, 24, 26, 52, and once every 6 months thereafter. Background immunosuppression, including doses of corticosteroids and MMF, may be adjusted at the investigator's discretion beginning at OLT Day 1.

During OLT, investigators should regularly review the study safety plan (see Section 5.1), including the risks associated with obinutuzumab (see Section 5.1.1) and management of specific adverse events that may be related to obinutuzumab (see Section 5.1.3.3), to ensure the patient has not developed a condition that would warrant discontinuation of obinutuzumab infusions. Prior to resuming OLT after treatment

interruption, investigators should refer to Section 5.1.3.2 to ensure the patient meets the criteria for resuming treatment.

After study unblinding (see Section 3.1.5), no further OLT will be initiated and ongoing OLT will be discontinued after OLT Week 52. Subsequent access to obinutuzumab may occur through post-trial access (see Section 4.3.4).

Patients who discontinue OLT will enter SFU (see Section 3.1.4).

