be combined for all primary and secondary comparisons between obinutuzumab and placebo. Descriptive comparisons only will be made between the obinutuzumab treatment arms.

As described in Section 3.1, dosing after Week 76 will be determined based on the investigator's assessment of adequacy of treatment response and need for intensification of therapy. This process will enable expanded access to obinutuzumab after Week 76 while maintaining study blinding and providing controlled, comparative data among patients with an adequate response who remain on blinded infusions.

Adequate Response

If the investigator assesses that 1) an adequate treatment response has been achieved, 2) there is no need to intensify therapy, and 3) there are no unmanageable treatment-emergent adverse events, it is appropriate to continue blinded infusions of obinutuzumab 1000 mg or placebo every 6 months.

Incomplete Response with Some Improvement

Patients who meet all of the following criteria, as assessed by the investigator, will be eligible for OLT:

- Inadequate treatment response
- Clinically meaningful improvement from baseline in renal parameters or prior clinically meaningful improvement from baseline followed by worsening
- Need for intensification of therapy
- No unmanageable treatment-emergent adverse events

During OLT, obinutuzumab 1000 mg will be administered on OLT Day 1 and OLT Weeks 2, 24, 26, and 52. Obinutuzumab 1000 mg will subsequently be administered every six months. Prior to initiation of OLT, documentation of these criteria will be submitted to the Medical Monitor for review. Investigators may discuss the appropriateness of OLT directly with the Medical Monitor if needed.

This open-label regimen is appropriate for eligible patients from all treatment groups without revealing the randomized treatment assignment:

For patients initially randomized to placebo, obinutuzumab induction represents an intensification of therapy with the potential for clinical benefit.

For patients initially randomized to obinutuzumab, eligibility criteria require that the patient has exhibited a clinically meaningful response to obinutuzumab and that there are no unmanageable treatment-emergent adverse events. Retreatment with obinutuzumab in these patients, regardless of the randomized obinutuzumab treatment regimen, is supported by published clinical data with rituximab and population PK modeling from NOBILITY as summarized below.

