4.3.1.1 Obinutuzumab and Placebo

Obinutuzumab 1000 mg or placebo will be administered by IV infusion during blinded treatment at Day 1 and Weeks 2, 24, 26, 50, and 52 as described in Section 3.1.2. Subsequent blinded infusions will occur at Week 80 and every 6 months thereafter for

patients with an adequate response at Week 76. OLT will follow the initial obinutuzumab treatment schedule with infusions on OLT Day 1; at OLT Weeks 2, 24, 26, 52, and every 6 months thereafter (see Section 3.1.3).

Instructions for the administration of obinutuzumab or placebo infusions are provided in Appendix 6.

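### The open-label schedule note pairs infusions at OLT Weeks 50 and 52, but the table it annotates and the protocol text list OLT Week 52 and no Week 50 visit

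*Protocol*

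**What the plan says.** The Notes under Table 3 of Protocol Appendix 1, which covers open-label treatment, first set a visit window of 3 days either side and then add that "an interval of 14 days should be kept between paired blinded obinutuzumab infusions". Three OLT pairs follow: Day 1 with Week 2, Week 24 with Week 26, and "OLT Days 350 (OLT Week 50) & 364 (OLT Week 52".

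The other statements of the OLT infusion weeks are:

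- Synopsis, Study Treatment: "infusions on OLT Day 1; at OLT Weeks 2, 24, 26, 52 and every 6 months thereafter".
- Section 3.1.3: "patients will receive obinutuzumab 1000 mg on OLT Day 1 and OLT Weeks 2, 24, 26, 52, and once every 6 months thereafter".
- Section 3.3.1: "obinutuzumab 1000 mg will be administered on OLT Day 1 and OLT Weeks 2, 24, 26, and 52", followed by six-monthly dosing.
- Section 4.3.1.1: "infusions on OLT Day 1; at OLT Weeks 2, 24, 26, 52, and every 6 months thereafter".
- Table 3 grid: visit columns at OLT Weeks 0, 2, 4, 12, 24, 26, 36, 52 and 76, then every 6 months. The administration row is marked at Weeks 0, 2, 24, 26, 52 and 76, and every 6 months after that.

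Elsewhere (Sections 3.1.5 and 4.3.2.2, Appendix 6), the only infusion named around OLT Month 12 is the one at OLT Week 52.

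**The concern.** The note sits in the schedule that sites work from, not in background text. It attaches specific day numbers to a second infusion around OLT Month 12 that no other statement of the OLT schedule contains. It also describes open-label infusions as blinded, which cannot be right for this table.

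One or two infusions at Month 12 is a real distinction in this trial. It is exactly what separates obinutuzumab Arm 1 (Weeks 50 and 52) from Arm 2 (Week 52 only). The Synopsis and Section 4.3.1.1 also say that OLT follows the initial obinutuzumab schedule. Blinded infusions in the initial period do include Week 50, so a reader of the note can find some support for it elsewhere, although the same sentences go on to list Week 52 alone.

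At stake are consistent dosing between sites in the open-label period and the exposure, pharmacokinetic and safety data collected there.

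**Working it through.** The plan states no figure to reproduce. The check sets the lists of infusion weeks side by side and counts infusions through OLT Week 52.

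| Source (Protocol) | OLT infusion weeks through Week 52 | Count |
|---|---|---|
| Synopsis | 0, 2, 24, 26, 52 | 5 |
| Section 3.1.3 | 0, 2, 24, 26, 52 | 5 |
| Section 3.3.1 | 0, 2, 24, 26, 52 | 5 |
| Section 4.3.1.1 | 0, 2, 24, 26, 52 | 5 |
| Appendix 1 Table 3, grid | 0, 2, 24, 26, 52 | 5 |
| Appendix 1 Table 3, Notes (pairs) | 0, 2, 24, 26, 50, 52 | 6 |

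1. **Are the day numbers in the note coherent?** 50 × 7 = 350, 52 × 7 = 364, and 364 − 350 = 14. The entry describes a genuine two-infusion pair, and a garbled table would not produce that.
2. **Which listed weeks lack a Table 3 column?** Only Week 50.
3. **Dose implied, at 1000 mg per infusion.** 5 × 1000 = 5000 mg; 6 × 1000 = 6000 mg. The difference is 1000 mg, and 1000 / 5000 = 20%. This applies per patient, through OLT Week 52 only, and only if the patient actually received an infusion at Week 50.
4. **What does the grid provide at Week 50?** No visit, and so no scheduled IxRS contact, vital signs, pregnancy test, pharmacokinetic sample or infusion. Table 3's footnotes require a negative pregnancy test before every infusion in women of childbearing potential, and samples before and after infusion at infusion visits.
5. **Where might the entry have come from?** The Notes to Table 1 (blinded period) carry the same three pairs without the OLT prefix, and there they match the blinded schedule. The amendment rationale says the interval wording was added to Tables 1 and 3 to standardise exposure, and mentions no additional OLT infusion. Carry-over from Table 1 is an inference, but the word blinded in an open-label table fits it.
6. **Can the Week 76 analyses be affected?** No. OLT starts at Week 80 at the earliest (Section 3.1.3), so OLT Week 50 falls no earlier than study Week 80 + 50 = 130.

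**The case against.** The strongest reply is that the note gives no dosing instruction. It follows directly from the visit-window rule and governs only the spacing between infusions scheduled elsewhere. The part of Table 3 that schedules infusions is the grid, and the grid has nothing at Week 50. A site acting on the note alone would need an unscheduled visit, and would depart from the grid, the Synopsis and three sections. The effect on analysis is also slight. The All Exposure safety analysis (SAP Section 4.6.7) runs from first dose to six months after the last dose or an earlier stop, so a Week 50 infusion followed by the Week 52 infusion moves neither end of that window.

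Most of this stands. It makes a discrepancy in practice unlikely and keeps the matter minor. It does not remove the contradiction: the note is current text, its day numbers are deliberate, and an interval rule for a pair presupposes that both infusions exist.

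A reader might go further and infer that sites will give an unplanned extra infusion, or that open-label patients should be expected to receive 20% more drug. The documents do not support either. No text instructs administration at OLT Week 50, and nothing indicates that any patient would receive it. Calling such an infusion extra would also presume which of the two schedules is intended, and only the sponsor can settle that.

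**Conclusion.** The protocol is wrong as written on this point, through an internal inconsistency of minor severity. The mismatch is certain because it rests on a direct comparison of current text. The consequence is conditional: a patient for whom the note was followed would have one more 1000 mg infusion through OLT Week 52 than under the other statements. That would bear on the patient's recorded exposure and on the pharmacokinetic and safety data from the open-label period. The number of patients who might be affected is not stated and cannot be derived from the documents. No Week 76 primary or secondary result depends on it. This review takes no view on which schedule is correct.

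**What to change.** The sponsor should:

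- confirm the intended OLT infusion visits;
- reconcile the Table 3 note with the Table 3 grid, the Synopsis and Sections 3.1.3, 3.3.1 and 4.3.1.1, so that all give the same visits;
- correct the word blinded in the open-label note;
- notify sites of the clarification.

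The cost is a short protocol clarification and a site notice. No statistical analysis needs to change.
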